### 16.2 Sample Size

On average, we recruit six patients per month for GBM treatment trials. For symptom control studies with heterogeneous populations, such as N05C7 (Concerta), we were able to average 25 patients a month. We have found that symptom management trials targeting symptoms with a high prevalence have rapid accrual. Therefore, for this study, a reasonable conservative estimate for this more homogeneous population would be 8 patients a month. With 330 patients, accrual would be completed in 41 months.

The randomized design to be utilized is described below. Based on our previous work, we estimate that the response rate for the placebo arm will be 10%. We design the study with 100 patients per arm so that the Fisher’s exact test will have 80% power to detect a response rate of 25% with a two-tailed alternative and a 5% Type I error rate for each treatment comparison to the placebo. Again, we are not using a conservative multiple contrasts approach because we want to err on the side of accepting a modest armodafinil effect. We plan to accrue an additional 30 patients to account for patient cancellations, ineligibility, or major treatment violations. Therefore, there will be a maximum of 330 patients accrued to this study unless undue adverse events are encountered.

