## APPENDIX X: BAYES SHADOW STATISTICAL DESIGN

### Bayes Shadow Statistical Design

The primary endpoint for the trial is the response rate in terms of a clinically meaningful improvement in patient-reported fatigue, defined as at least a two-point improvement in fatigue as measured by the worst fatigue item from the Brief Fatigue Inventory at 8 weeks, and the design proposed for this study will randomize a minimum of 30 evaluable patients and a maximum of 120 evaluable patients to one of three treatment arms. The Bayesian adaptive randomization design (98) will work as follows. The first 30 patients will be randomized in a 1:1:1 fashion to the three treatment arms (block size of 30 will be used to guarantee an equal number of patients are randomized to each treatment arm). After the 30th patient has been randomized, the adaptive randomization procedure will begin. As a shadow design, we will use the data from the completed Fisherian design and then assess the different assignations that would have been made via the Bayes design and its impact on the trial results.

Adaptive randomization: We assume that the fatigue response outcome, denoted  $X_{i,j}$ , of patient  $i$  on treatment  $j$  derives from a  $\text{Binomial}(\pi_j)$  distribution ( $j=1$  for placebo;  $j=2$  for armodafinil 150 mg). We assume that  $\pi_j$  derives from a Beta  $(\alpha_j, \beta_j)$  distribution. Given limited historical data, we use a uniform non-informative prior for each arm ( $\alpha_1=\alpha_2=1$ ;  $\beta_1=\beta_2=1$ ). We repeat this calculation for the comparison of the placebo versus the armodafinil 250 mg arm and normalize the result to get three probabilities for treatment assignation.

As each patient is enrolled, the randomization probability for each treatment arm is recomputed using all currently available fatigue response data from already accrued patients. The randomization procedure computes the posterior probability for each treatment of being the best between the two treatments (where  $p_j$  = probability that treatment  $j$  is better than the other treatment) and assigns the patient to arm  $j$  with probability  $p_j$  (i.e.,  $\lambda=1$  in the notation of Cook [100]). This procedure uses all observed fatigue response data at the time of the patient's randomization to unbalance the randomization probabilities in favor of the treatment arm having comparatively superior symptom response outcomes.

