Efficacy stopping rules: If at any time prior to full accrual the probability that an arm is superior to the other arm given all available data falls below 0.05 ( $P_L$  in the notation of the Adaptive Randomization software used below), that arm is suspended (though it potentially could reopen should the results on the other arm substantially worsen). If at any time prior to full accrual the probability that an arm is superior to the other arm given all available data rises above 0.95 ( $P_U$  in the notation of the Adaptive Randomization software used below), that arm is declared the winner and the trial is stopped early.

Decision rule: If the trial runs through completion without early stopping and if the largest probability for the two armodafinil treatment arms is better than that for the placebo arm is greater than 0.80 ( $P_U^*$  in the notation of the Adaptive Randomization software used below), then that treatment is declared the winner of the trial.

Operating characteristics: Operating characteristics of a clinical trial with the above parameters and accrual rate were simulated (10,000 replicates) using software developed by the M. D. Anderson Cancer Center Department of Biostatistics (available at:<http://biostatistics.mdanderson.org/SoftwareDownload/>):

Arm 	True Confirmed Fatigue Response Rate	Pr(Selected) 	Pr(Selected Early) 	Pr(Stopped Early) 	Average Number of Evaluable Patients Treated	Average Trial Duration
1	10%	0.20	0.07	0.07	34	27.6 mo
2	10%	0.20	0.07	0.07	34	
1	10%	0.09	0.04	0.21	29	26 mo
2	15%	0.41	0.19	0.04	36	
1	10%	0.03	0.02	0.39	24	23.5 mo
2	20%	0.63	0.36	0.02	35	
1	10%	0.02	0.01	0.57	20	20.4 mo
2	25%	0.80	0.54	0.01	33	
1	10%	<0.01	<0.01	0.73	18	17.4 mo
2	30%	0.90	0.69	<0.01	29	

1. 1=placebo, 2=best of armodafinil arms.
2. The overall probability that the given arm is selected as being the best treatment after the trial has ended.
3. The probability that the given arm is selected as being the best treatment arm early (prior to all patients being enrolled).
4. The probability that the given arm is dropped for any reason (due to futility or another arm being selected).

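### The Appendix X operating-characteristics table does not describe the three-arm, 120-patient shadow design it is said to come from

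*Combined protocol and SAP*

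**What the plan says.** Appendix X states that the shadow design "will randomize a minimum of 30 evaluable patients and a maximum of 120 evaluable patients to one of three treatment arms", and that "The first 30 patients will be randomized in a 1:1:1 fashion to the three treatment arms". After the run-in, allocation becomes adaptive. For the priors, "we use a uniform non-informative prior for each arm". Placebo is compared with each dose in turn, and the instruction is then to "normalize the result to get three probabilities for treatment assignation". An arm is suspended when its probability of being superior falls below 0.05 and wins early above 0.95. At the end, the better dose wins if its probability of beating placebo exceeds 0.80.

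The table is introduced with "Operating characteristics of a clinical trial with the above parameters and accrual rate were simulated (10,000 replicates"). It has two rows per scenario, labelled "1=placebo, 2=best of armodafinil arms". Appendix X gives no accrual rate. The only rate planned for this trial is in Section 16.2: "a reasonable conservative estimate for this more homogeneous population would be 8 patients a month".

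Section 16.1 explains the purpose. The completed trial's data will be used to see what the Bayes design would have done, as a feasibility exercise to inform future cancer control trials.

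**The concern.** The table is the only statement of the shadow design's false-selection rate, power, size and duration. Section 16.1 gives the potential advantage of the Bayes approach as earlier completion with fewer patients at risk, and these are the columns a reader would use to judge that. If the table belongs to a smaller trial with fewer arms, the comparison with the 330-patient, 41-month trial uses the wrong benchmarks, and later designs could inherit them.

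The text suggests how this could happen. The model defines only j=1 (placebo) and j=2 (150 mg), and the allocation and stopping rules still speak of two treatments and of the other arm. The 250 mg arm enters in a single added sentence.

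**Working it through.** **Inputs.** From Appendix X: three arms, run-in 30, maximum 120, uniform priors, cut-offs 0.05/0.95/0.80 and an 8-week outcome (56/30.4 = 1.84 months). From Section 16.2: 8 per month, and 330 accrued for 300 evaluable.

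**1. Patient numbers, all arms at 10%.** Early selection is 0.07 + 0.07 = 0.14. If the other 86% of trials run to 120 and none stops before 30, the mean total is at least 0.86 × 120 + 0.14 × 30 = 107.4. The table shows 68. Solving 0.86M + 0.14E = 68 for the maximum M gives 75.8, 74.2 and 72.6 when early stops average E = 20, 30 and 40 patients. None of this depends on accrual rate.

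**2. Could a third arm be unprinted?** If it too were selected early 7% of the time, the bound is 0.79 × 120 + 0.21 × 30 = 101.1, so it would hold at least 33 patients. Three arms of 34 (102) would then just be possible if early stops averaged (102 − 94.8)/0.21 = 34 patients. But footnote 4 counts an arm as stopped early whenever another arm is selected, so placebo's figure would be about 0.14. It is 0.07, equal to arm 2's early selection alone. If instead the third arm is almost never selected early, the bound returns to 107.4 and that arm needs about 39 patients, more than the 34 on the best dose. In all five scenarios arm 2's early stopping equals arm 1's early selection (0.07, 0.04, 0.02, 0.01, <0.01), again with no sign of a third arm.

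**3. Duration.** Full enrolment plus the last outcome takes 120/8 + 1.84 = 16.8 months. If 120 evaluable means 132 accrued, it is 132/8 + 1.84 = 18.3 months. The printed means are 27.6, 26, 23.5, 20.4 and 17.4: all five exceed 16.8 and four exceed 18.3. Printed patients divided by printed months give 2.5 to 2.7 per month.

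**4. Reproducing the table.** A two-arm simulation (maximum 72, run-in 20, 2.6 per month, 3,000 replicates; simulation error up to about 0.01) compares with the table as follows:

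| Arm 2 rate | Arm 2 selected: simulated / printed | Arm 2 selected early | Arm 1 stopped early | Total patients | Months |
|---|---|---|---|---|---|
| 10% | 0.20 / 0.20 | 0.07 / 0.07 | 0.07 / 0.07 | 67.5 / 68 | 27.6 / 27.6 |
| 15% | 0.41 / 0.41 | 0.17 / 0.19 | 0.17 / 0.21 | 65.1 / 65 | 26.6 / 26 |
| 20% | 0.64 / 0.63 | 0.34 / 0.36 | 0.34 / 0.39 | 59.6 / 59 | 24.2 / 23.5 |
| 25% | 0.79 / 0.80 | 0.54 / 0.54 | 0.54 / 0.57 | 52.0 / 53 | 21.1 / 20.4 |
| 30% | 0.90 / 0.90 | 0.67 / 0.69 | 0.67 / 0.73 | 46.3 / 47 | 18.6 / 17.4 |

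Two arms with a maximum of 120 do not fit: the null total is 107, and selection is 0.24 per arm under the null and 0.90 at 25%.

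**5. The design as described** (three arms, maximum 120, 8 per month; 2,000 replicates pairwise, 1,000 best-of-three):

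| Reading | Doses at 25% (others 10%) | Selected: placebo / dose A / dose B | Total patients | Months |
|---|---|---|---|---|
| Pairwise with placebo | none | 0.08 / 0.17 / 0.17 | 109 | 15.2 |
| | A | 0.01 / 0.82 / 0.05 | 81 | 10.9 |
| | A and B | 0.00 / 0.47 / 0.48 | 70 | 9.3 |
| Best of three | none | 0.04 / 0.04 / 0.04 | 117 | 16.4 |
| | A | 0.01 / 0.67 / 0.00 | 104 | 14.3 |
| | A and B | 0.00 / 0.19 / 0.17 | 110 | 15.2 |

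The pairwise result depends on how placebo's two probabilities are combined before normalising, which Appendix X does not say. Taking their mean, sum, minimum or product gave null selection of either dose of 35%, 37%, 33% and 28% (800 replicates each). Across all runs the range was about 27% to 37%.

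**The case against.** Several points on the other side stand.

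- **The source is inferred.** A reader might conclude that the table definitely comes from a two-arm, 72-patient run. The documents never say so, and the fit is imperfect. In a strict two-arm trial arm 1's early stopping should equal arm 2's early selection, yet the table shows it 0.02 to 0.04 higher in four scenarios, and simulated durations differ by up to 1.2 months.
- **Duration is the weaker evidence.** The 8 per month was planned for the Fisherian trial. At 6 per month, the rate Section 16.2 gives for GBM treatment trials, the bound is 21.8 months (23.8 with 132 accrued), and only three (two) means exceed it. At 4 per month the three-arm pairwise design averages 29.2 months under the null and 20.1 with one dose at 25%, not far from 27.6 and 20.4. That version still fails on placebo selection under the null (0.06 against 0.20) and early selection at 25% (0.67 against 0.54).
- **Identical null rows are not decisive alone.** If 'best' means one designated dose, a symmetric three-arm rule also gives equal rows. The mismatch rests on those rows together with the totals and the early-stopping column.
- **The 80% is not simply wrong.** On the pairwise reading with exactly one effective dose, selection is about 82%. The 36% to 67% figures need a best-of-three rule, whereas the stated final rule compares doses with placebo.
- **The 20% might be per dose.** The pairwise per-dose rate is 0.17 to 0.18. But the row is labelled as the best of the two doses, so a reader will take it as the chance that armodafinil wins.

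It is also fair that no patient is allocated, and no arm stopped, from this table.

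**Conclusion.** The point holds in this form: the printed false-selection rate, patient numbers and durations do not describe the three-arm, maximum-120 design that Appendix X sets out. The patient count and early-stopping columns show this without any assumption about accrual. The durations add support if accrual is 8 per month.

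On the pairwise reading, false selection of either dose is roughly 27% to 37% against the printed 20%, and the null mean is about 110 patients against 68. No single replacement percentage can be given until the normalisation is specified. The 80% figure is approximately right on that reading only when one dose works; with both at 25%, some dose is selected in about 92% to 95% of trials. A two-arm source with a maximum of about 72 at 2.6 to 2.7 per month is the best explanation found, not a documented fact.

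A reader might infer that the trial's power or its primary comparison is affected. It is not: Sections 16.2 and 16.3 rest on Fisher's exact test with 100 patients per arm, and the shadow design is applied afterwards to completed data. The harm is confined to what is reported about the Bayes design.

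**What to change.** Re-simulate the three-arm, maximum-120 design and replace the table. State the normalisation of the assignment probabilities, the decision rule as applied to three arms, the accrual rate, and whether 120 counts evaluable or accrued patients. Report all three arms, with scenarios for no, one and both doses effective, and give the probabilities of selecting placebo, each dose and either dose. Do not write in a fixed false-selection figure in advance, because it depends on those choices.

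Alternatively, keep the table but label it as a two-arm illustration, if the sponsor's records confirm that, with its actual maximum sample size and accrual rate. Do not cite it as the shadow design's properties.

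The cost is a few hours of simulation and, on the pairwise reading, a less favourable stated false-selection rate. Enrolment, treatment and the primary analysis do not change.

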## **APPENDIX XI: SITE DRUG ORDERING INSTRUCTIONS AND ORDER FORM**

### **Site Ordering Instructions and Order Forms: Armodafinil and Placebo**

**Background:** The NCCTG/Alliance research base pharmacy will deviate from their standard operational policy of supplying study agent to the main NCCTG, CALGB and ACOSOG memberships. For this trial, the research base pharmacy will send one patient specific supply (one bottle) directly to each participating main membership or each participating affiliate site upon receipt of an order from the participating site. This order must be completed each time a study participant is enrolled.

**Starter Supplies:** **Each treating location, must request one patient-specific bottle each time a patient is registered in the trial by completing the Alliance Clinical Order/Return Form located on page 2 of this appendix. Note a sample form is included (page 3 of this appendix)**

Please be certain to include a *complete shipping address* for the treatment site.

Please include your ***patient's registration number and initials on the form***. Please also include the DEA Registration Number of your Pharmacy or investigator on the order form.

The site must also complete the Alliance clinical drug order/return form located on page 2 of this appendix, and fax it to the number listed on the form.

A221101	2XXXXXX	Example: ABC	armodafinil 150mg or armodafinil 250mg or placebo tablets	56 tablets per bottle	One bottle	XX/XX/XXXX				
SHIPPING ADDRESS:  Site Name: Facility: Department: Street Address: City, State: Zip:			NOTE: Urgent Shipments must be accompanied by an express courier account number.  Express Courier Name:  Express Courier Acct No.: _____			INSTRUCTIONS: 1. One item or protocol per line 2. When requesting drugs: Fill in all sections completely, except shaded areas. 3. When returning drugs: Fill in all sections completely, including shaded areas. 4. Must include official shipping address. 5. Sign and date the order/return.				

Page 3 of 3

## **APPENDIX XII: NURSE/CRA PHONE CONTACT**

### **Nurse/CRA Phone Contact Guide**

Patient Phone No. \_\_\_\_\_  
Best Dates/Times to call \_\_\_\_\_

#### **FOLLOW UP:**

Phone call schedule: Call patient at home the end of study weeks 4 and 8. This is to remind patient to take the study agent as instructed, document compliance, encourage completion of the booklet, and address problems. If the patient is seen in clinic, this phone call can be omitted.

•  
3. Items to document:

- Date of phone call
- Study week
- Questions/Comments
- Performance Status Score
- AE assessment end of weeks 4 and 8

If the patient reports any side effects, please document:

- o Side effects:
  - Headache
  - Any others - Severity and attribution, if applicable.

4. Reinforce compliance with study medication.

5. Reinforce completion of questionnaires and request return of them at end of the month.

**APPENDIX XIII: GODIN LEISURE TIME EXERCISE QUESTIONNAIRE (GLTEQ)**

--	--	--

Patient ID

MDS Study

--	--	--

Patient Initials

Godin Leisure - Time Exercise Questionnaire

Baseline    Post Treatment

---

1. Considering the **previous 7-Day period (this past week)**, how many times did you do the following kinds of exercise for **more than 15 minutes** during your **free time**.

a) **STRENUOUS EXERCISE (HEART BEATS**

**RAPIDLY) (i.e. running, jogging, hockey, football, soccer, squash, basketball, cross country skiing, judo, roller skating, vigorous swimming, vigorous long distance bicycling, spinning)**

--

b) **MODERATE EXERCISE (NOT EXHAUSTING)**

**(i.e. fast walking, baseball, tennis, easy bicycling, volleyball, badminton, easy swimming, alpine skiing, popular and folk dancing, yoga, tai chi, pilates)**

--

c) **MILD EXERCISE (MINIMAL EFFORT) (i.e. archery, fishing from river bend, bowling, horseshoes, golf, snow-mobiling, easy walking)**

--

2. Considering the **previous 7-Day period (this past week)**, during your leisure-time, how often did you engage in any regular activity long enough to work up a sweat (heart beats rapidly)?

often

sometimes

never/rarely

**APPENDIX XIV: PRO-CTCAE**

**PRO-CTCAE Questionnaire**

**PRO-CTCAE items for fatigue and cognitive function**

1. In the last 7 days, what was the SEVERITY of your fatigue, tiredness, or lack of energy at its WORST:

None / Mild / Moderate / Severe / Very severe

2. In the last 7 days, how much did fatigue, tiredness, or lack of energy INTERFERE with your usual or daily activities:

Not at all / A little bit / Somewhat / Quite a bit / Very much

3. In the last 7 days, what was the SEVERITY of your problems with concentration at their WORST:

None / Mild / Moderate / Severe / Very severe

4. In the last 7 days, how much did problems with concentration INTERFERE with your usual or daily activities:

Not at all / A little bit / Somewhat / Quite a bit / Very much

5. In the last 7 days, what was the SEVERITY of your problems with memory at their WORST:

None / Mild / Moderate / Severe / Very severe

6. In the last 7 days, how much did problems with memory INTERFERE with your usual or daily activities:

Not at all / A little bit / Somewhat / Quite a bit / Very much

## APPENDIX XV: ECOG PERFORMANCE SCORE

### ECOG PERFORMANCE STATUS

#### Grade

0	Fully active, able to carry on all predisease activities without restriction (Karnofsky 90-100).
1	Restricted in physically strenuous activity but ambulatory and able to carry out work of a light or sedentary nature, e.g., light housework, office work (Karnofsky 70-80).
2	Ambulatory and capable of all self-care, but unable to carry out any work activities. Up and about more than 50 percent of waking hours (Karnofsky 50-60).
3	Capable of only limited self-care, confined to bed or chair 50 percent or more of waking hours (Karnofsky 30-40).
4	Completely disabled. Cannot carry on any self-care. Totally confined to bed or chair (Karnofsky 10-20).
5	Dead

